3. STUDY ENDPOINT

The primary hypothesis is that the administration of advanced hemodynamic monitoring utilizing the Hypotension Prediction Index (HPI) with a protocolized strategy during moderate-to-high-risk noncardiac surgery reduces composite of severe postoperative complications.

3.1 Primary Effectiveness Endpoint

The primary objective of this study is that the administration of a protocolized strategy utilizing advanced hemodynamic monitoring with a hypotension prediction index software reduces composite of severe postoperative complications identified within 30 days post-operative period.

The primary outcome variable is a composite endpoint that includes major adverse cardiac events (MACE), acute kidney injury (AKI), and serious infection (pneumonia, deep surgical site, sepsis, and organ space surgical site infection).

Myocardial injury will be diagnosed based on troponin concentrations preoperatively. MINS is defined as any myocardial infarction (i.e., 4th Universal Definition of myocardial infarction¹⁷), and any elevated troponin judged to be due to myocardial ischemia (i.e., without evidence of a non-ischemic etiology, e.g. chronic elevation, pulmonary embolism, sepsis, cardioversion, others) that occurred within the first 30 days after surgery. Strokes will be detected from clinical symptoms lasting at least 24 hours. Mortality is confined to a 30-day post-operative window. Postoperative acute kidney injury will be defined by the Kidney Disease Improving Global Guidelines (KDIGO). Surgical infection site (pneumonia, deep surgical site, and organ space) within 30 days after the operative procedure is defined according Clavien-Dindo grade II or greater. Please see the study protocol for more detailed criteria.

3.2 Exploratory Analysis Datapoints

The following measures will also be investigated for this study:

1. Time-to-Adverse Event (Complications) Analysis
 - a. Non-Parametric Survival Analysis (KM approach)
 - b. Cox Proportional Hazard Model
 - c. Mixed effect Cox Proportional Hazard Model
 - d. Stratification analysis through applying study sites, gender, race as the stratification factor
 - e. Fixed/Mixed effective Poisson regression model applying the count of events as the response
 - f. Mixed effective survival model to assess the multiple event cases within patient

 Edwards	Revision Date: May 11, 2022	Rev	A	For Use Only by Affiliates of Edwards Lifesciences	Page 8 of 19
	Title	Statistical Analysis Plan for HPI SMART-BP Trial			

2. Hypotension management analysis
 - a. Time from alert event to intervention
 - b. % alerts with no intervention
 - c. Reasons for nonintervention
 - d. Amount of hypotension removing nonintervention segments
 - e. Agreement analysis; clinical decision vs. treatment algorithm
 - f. Overall treatment protocol compliance
3. Hypotension duration (minute) is the summation of hypotension instance duration, defined as the consecutive measurements with MAP<65 lasting at least 1 minute.
4. Area under the curve (AUC) with the MAP threshold of 55,65,75 mmHg
5. Time Weighted Average (TWA) of intraoperative hypotension (mmHg)
6. Time in target SVV <13% (for valid SVV readings = no arrhythmia)
7. Time in target CI >2.5 L/min/m15
8. Postoperative morbidity survey (POMS) on postoperative day 3
9. Transfusion requirement (mL packed red blood cells)
10. Amounts of intraoperative crystalloid and colloid and vasoactive drugs; mL
11. Amount of vasoactive drugs; mg (e.g.: phenylephrine, ephedrine, norepinephrine, epinephrine, dobutamine)
12. Amount of intraoperative intravenous analgesics and sedatives
13. Brain oxygen saturation – StO2 using ForeSight Elite tissue oximetry system, time in target
14. Verification of the incidence of the listed postoperative complications may be performed at each site by reviewing historic data up to 6 months prior to study initiation
15. Cost of care
16. Hospital length of stay
17. Hospital readmission within 30 days

Please see appendix section 12.9 for TWA calculation.

4. ANALYSIS POPULATIONS

4.1 Modified Intent-to-treat (mITT)

Modified Intent-to-treat (mITT) is defined as the study subjects who were exposed to the study product and will therefore be included in the effectiveness and safety analysis datasets. All randomized study subjects who have satisfied the population criteria will be classified in the designated population and will only be included in analyses for which they have available data. The mITT population will also be used to present exploratory analyses by the randomized treatment arm. The safety population is defined as all randomized subjects who were exposed to the study product; thus, the safety population will therefore be identical to the mITT population if all randomized subjects are exposed to the study product. In this clinical study, the primary effectiveness endpoint is a composite measurement of MINS, AKI, and serious infection adverse events, mITT will be the target population in interim, and final effectiveness analysis. The Roll-in subjects designed for the training purpose to avoid a learning curve bias will be analyzed separately. The safety population will be used to present the safety summaries by actual treatment received.

 Edwards	Revision Date: May 11, 2022	Rev	A	For Use Only by Affiliates of Edwards Lifesciences	Page 9 of 19
	Title	Statistical Analysis Plan for HPI SMART-BP Trial			

4.2 Full Analysis Population (FAS)

The full analysis population is defined as all pivotal subjects with valid intra-operative measurements during non-cardiac surgery, and with at least one valid post-operative measurement. It will be applied in primary and secondary effectiveness sensitivity analysis.

4.3 Per Protocol Population (PP)

A per protocol analysis population is defined as a group of pivotal subjects who enrolled into study and completed all operations as written in the protocol (e.g., No major protocol deviations occurred during the non-cardiac surgical procedures). It will be applied in primary and secondary effectiveness sensitivity analysis.

4.4 Complete (Evaluable) Case Population (CC)

The complete case population is defined as all pivotal subjects who complete surgery, have valid post-operative data and follow-up records, and exit this study by designed procedure within protocol. It is the population used in primary and secondary effectiveness endpoint sensitivity analysis in final analysis.

4.5 Roll-in Subject

To prevent a learning curve bias, up to five (5) Roll-in cases may be performed at a site, as needed, with a maximum total of 60 Roll-in cases in the Trial. Roll-in cases will be analyzed separately from the pivotal cohort.

4.6 Screen Failures

Late screen failures are defined as subjects who consent to participate in the clinical trial and but are not subsequently randomly assigned to the trial intervention or entered in the trial. So, the subjects are not exposed to FloTrac sensor or Acumen IQ sensor and are not treated as part of the study. Late screen failures will be represented in summary tables by counts and percentages. Please see study protocol for more detailed criteria.

5. DEFINITIONS

5.1 Analysis Dates and Days

Subjects who fulfill all eligibility criteria will be scheduled for surgery and followed for 30 days post-surgery. The 30-day follow-up has a ± 14 -day window (see protocol for more detailed information). Pre-procedure data collection includes: (1) Pre-op Surgical Risk Assessment, and (2) the lab values: creatine, troponin, and NT-proBNP. On post-op day 1 the following data will be collected: (1) the lab value troponin, (2) post-op complication, and (3) fluid and vasoactive medications. On post-op day 2 the following data will be collected: (1) the lab values: creatinine and troponin, (2) adverse events, and (3) post-operative complications. The POMS will be given on postoperative day 3, further, the POMS may be entered into the system until after the third day. Other post-op day 3 data include: (1) the lab value troponin, (2) Post-Op Neurocognitive Assessments, (3) post-op complications, (4) adverse events, and (5) post-op complications. Lastly, for 30-day follow up the following will be evaluated: (1) post-op complications, (2) adverse events, and (3) the WHODAS 2.0 survey.

5.2 Analysis Window

There is no analysis window for this study. Please see the protocol for more detailed procedure information.

 Edwards	Revision Date: May 11, 2022	Rev	A	For Use Only by Affiliates of Edwards Lifesciences	Page 10 of 19
	Title	Statistical Analysis Plan for HPI SMART-BP Trial			

6. DATA AND ANALYSIS CONVENTIONS

6.1 General Conventions

The baseline characteristics and demographics, the medical history data of each study subject will be collected during the subject screening process and recorded on an electronic case report form (eCRF). The hemodynamic measurement data will be downloaded from HemoSphere advanced monitoring platform.

All endpoints will be presented using descriptive statistics by assigned treatment group; continuous variable will be summarized with the mean, standard deviation (SD), median, and interquartile range (IQR); binary and categorical variables will be presented using count and percentage.

Other summaries (e.g., minimum, maximum, standard error, 95% intervals, coefficient of variation (CV) or %CV, odd ratio) will be used as appropriate. Sample sizes shown with summary statistics are the number (n) of patients with non-missing values. All percentages should be rounded and reported to a single decimal place (xx.x%). If percentages are reported as integers, percentages greater than 0% but <1% will be reported as <1%, whereas percentages greater than 99% but <100% will be reported as >99%. A percentage of 100% will be reported as 100%.

For categorical endpoints, logistic regression and the approximate Z test will be performed on the primary outcomes and exploratory analysis. Summary statistics and p-values from the statistical comparison will be displayed in result report. The p-value will present with three decimals. P-values less than 0.001 will be reported as <0.001. Additionally, ad-hoc analyses may be conducted as deemed appropriate.

An independent Data Safety Monitoring Board (DSMB) will evaluate the data at interim.

6.2 Handling of Missing Data

Missing data are defined as those instances in which data collection was attempted yet failed for some reason (i.e., due to technological, procedural, and/or subject dropout). Demographic and baseline characteristics are collected from the study subjects as part of screening. Subjects who do not meet all criteria will not be enrolled into this study. Subjects who are not randomized are considered as screening failures. Data for screening failure subject will not be captured.

If missing data are not related to the subject's eligibility criteria, missing data will be presented as not reported in the demographic and baseline characteristics summary statistics table. These subjects will be included in all analysis. However, if the missing data are related to the subject's eligibility, this will be considered a protocol deviation, and in this case, the study data from this subject will be reviewed internally, to determine if the subject should be excluded from analysis set.

The hemodynamic measurements are downloaded from the monitor platform. Theoretically, there should be no missing data. If there are missing values in the hemodynamic parameters download from monitor platform caused by any reason, the last value will be carried forward.

For binary or categorical data that are missing as defined above, single imputation will be used. For continuous data that are missing as defined above, statistical imputation using the multiple imputation (MI) method.

By the data from similar clinical trial sponsored by Edwards LifeSciences, missing value of the primary effectiveness endpoint is really rare (less than 1%). In case, more than 5% study subjects with missing primary effectiveness endpoint, imputation techniques with different missing mechanisms (multiple imputation approach with assumption missing at complete random, missing at random, or tipping point analysis approach for missing not at random), mentioned in National Research Council publication ^[18], will apply to impute the missed values. Sensitivity analysis for primary

 Edwards	Revision Date: May 11, 2022		Rev	A	For Use Only by Affiliates of Edwards Lifesciences	Page 11 of 19
	Title	Statistical Analysis Plan for HPI SMART-BP Trial				

effectiveness endpoint will conduct on pivotal mITT data with imputed values to check the robustness of statistical analysis outcome.

With assumption missing primary effectiveness endpoint at random or complete at random (missing primary effectiveness endpoint unrelated to the actual value of primary effectiveness endpoint), 20 different datasets will be exported from multiple imputation approach. With exact the same statistical analysis method, the p value from the sensitivity analysis on imputed data should be consistent to the statistical hypothesis test result with valid pivotal mITT dataset.

With tipping point analysis approach for the missing primary effectiveness endpoint related to actual primary endpoint value, multiple imputed datasets are exported corresponding to all possible imputations. By the p-value from statistical analysis on all these imputed datasets, if a reasonable majority of statistical hypothesis tests have the same outcome as it from valid pivotal mITT dataset statistical hypothesis test, this statistical outcome would be considered robust.

Please see section 8.3 and 8.4 for outliers and sensitivity analysis.

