8.4 Sensitivity Analysis

Sensitivity analysis will be performed for primary endpoint. For primary effective endpoint, sensitivity analysis will be conducted with all study subjects from FAS, PP, or CC population to check if the similar conclusion could be drawn. If there are more than 5% study subjects with missing primary endpoint in test arm, the imputed endpoint with missing at complete random, or missing not at random will replace the missing value for each study subject, the sensitivity analysis on this imputed mITT pivotal dataset will be conducted to check if the similar conclusion could be drawn. Then check if the variation among study sites will affect the statistical comparison between study arms. Next check if the study cohorts (roll-

 Edwards	Revision Date: May 11, 2022		Rev	A	For Use Only by Affiliates of Edwards Lifesciences	Page 14 of 19
	Title	Statistical Analysis Plan for HPI SMART-BP Trial				

in, pivotal) will change the analytical conclusion. Finally, bootstrap approach will be applied to check if sample size effect the analytical result.

The effect of the following factors on the primary effectiveness endpoint will be analyzed:

- MAP threshold (<55, 60, 70 mmHg) and the length of time in hypotension episode definition (20, 40, and 80 seconds)
- NSQIP score vs ASA score
- Regional anesthesia vs general anesthesia
- Surgery technique (open or laparoscopic) vs hemodynamic changes
- Patient positioning vs hemodynamic changes
- Surgery type vs hemodynamic changes
- Survival analysis
- Arterial line vs Arterial line + CVP monitoring
- Onset of HPI Alert vs time of intervention
- Amount of vasopressors/fluids/inotropes administered vs time of intervention (start & stop time)
 - Stratified by cohort
- Tidal volume

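### SAP 6.2 sets unspecified single imputation for all missing binary data without exempting the binary primary, which conflicts with the observed-data rule at or below 5% missing

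*Combined protocol and SAP*

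**What the plan says.** SAP 6.2 opens with a broad definition: "Missing data are defined as those instances in which data collection was attempted yet failed for some reason", with subject dropout listed among the reasons. For data missing in that sense it gives two general rules. Continuous variables receive multiple imputation. For the rest, "For binary or categorical data that are missing as defined above, single imputation will be used". No single-imputation method is named.

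The primary then gets its own text. The sponsor expects fewer than 1% of primary outcomes to be missing. "In case, more than 5% study subjects with missing primary effectiveness endpoint, imputation techniques with different missing mechanisms" are to be applied, including multiple imputation and tipping point. The resulting sensitivity analysis of the primary "effectiveness endpoint will conduct on pivotal mITT data with imputed values to check the robustness of statistical analysis outcome". The multiple-imputation result, from 20 datasets, is to be compared with the "statistical hypothesis test result with valid pivotal mITT dataset". SAP 8.4 repeats the trigger on a different base: "If there are more than 5% study subjects with missing primary endpoint in test arm".

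For the main test, SAP 8.1 uses pivotal mITT subjects, and SAP 4.1 says that randomized subjects "will only be included in analyses for which they have available data". Protocol section 7 (Analysis Methods) computes the z-statistic on complete cases. SAP 4.4 reserves the complete-case population for sensitivity analysis.

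**The concern.** The primary outcome is binary (composite event or not), and a missed 30-day contact is missing data as 6.2 defines it. On its wording, the single-imputation rule therefore reaches the primary. The text specific to the primary says what is added above 5% missing. It does not say what the main test does with a missing outcome at or below 5%. There, 6.2 read literally fills the value in, while 4.1 leaves the subject out. Two programmers following the same SAP could produce different primary results, and a confirmatory test with fixed boundaries should not leave that open.

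Two kinds of harm are possible, depending on the unnamed fill:

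- A random draw treated as observed makes the standard error too small.
- A fixed value can shift the comparison when missingness differs between arms.

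Other binary outcomes, such as 30-day readmission, fall under the same general rule with no special text of their own.

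**Working it through.** **Inputs.** Control rate 0.31 (SAP 2.3). 1426 subjects without roll-ins (protocol section 7), randomized 1:1, so 713 per arm. One-sided overall alpha 0.025 and critical values, in absolute size, of 2.96259, 2.35898 and 2.01404 at 50%, 75% and 100% information (SAP 2.3). The fill methods and missingness patterns below are assumptions, because the SAP gives none.

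**The plan's own figure.** The probability under the null of crossing any of the three boundaries, ignoring futility, is 0.0250. This reproduces the stated alpha. The final look alone has a nominal one-sided level of 0.0220.

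**Case 1: one random draw from the arm rate.** Let a share m be missing completely at random in each arm of size n. The observed rate rests on n(1−m) subjects and the draws add their own noise, so the true variance is proportional to 1/[n(1−m)] + m/n. The analysis that treats fills as observed uses 1/n. The variance ratio is 1/(1−m) + m, and the naive standard error is the true one divided by the square root of that ratio.

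- m = 0.01: 1.0101 + 0.01 = 1.0201; naive/true SE = 0.990.
- m = 0.03: 1.0309 + 0.03 = 1.0609; naive/true SE = 0.971.
- m = 0.05: 1.0526 + 0.05 = 1.1026; naive/true SE = 0.952.

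The actual error is P(Z > c × naive/true SE):

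| Missing | Single test, c = 1.96 (nominal 0.025) | Final look, c = 2.01404 (nominal 0.0220) | All three looks (nominal 0.0250) |
|---|---|---|---|
| 1% | 0.0262 | 0.0231 | 0.0263 |
| 3% | 0.0285 | 0.0253 | 0.0289 |
| 5% | 0.0310 | 0.0276 | 0.0316 |

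The three-look column assumes the same missing share at each look. A simulation of the final look with 400,000 runs gave 0.0229 at 1% and 0.0276 at 5%. The available-case test in the same runs gave 0.0221 and 0.0220.

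**Case 2: fixed fill of no event, equal random missingness.** Each filled outcome is still a simple binary variable, with rate 0.31(1−m) in both arms, so the usual variance is right and the two arms agree under the null. Simulation with 1,000,000 runs gave a one-sided error at 1.96 of 0.0249 at 1% and 0.0252 at 5%. There is no inflation.

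**Case 3: fixed fill of no event, unequal missingness, no true effect.** With 5% missing in treatment and none in control, the filled rates are 0.31 × 0.95 = 0.2945 and 0.31. The difference is 0.0155. The standard error is √[(0.31×0.69 + 0.2945×0.7055)/713] = 0.0243. Z shifts by 0.0155/0.0243 = 0.64, and the final-look error is P(Z > 2.01404 − 0.64) = 0.084. With 4% against 1%, the rates are 0.2976 and 0.3069, the shift is 0.38 and the error is 0.051. With the arms reversed, the same shifts work against the treatment arm.

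In both patterns 2.5% of subjects are missing overall, so the trigger in 6.2 is not met. Nor is the test-arm trigger in 8.4, since neither 5% nor 4% exceeds 5%.

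**The case against.** The strongest reply is that the plan, read as a whole, does not impute the primary in its main test. SAP 4.1 includes subjects only where data are available. SAP 6.2 treats imputed runs of the primary as robustness checks against a test on valid data. SAP 6.1 reports sample sizes as patients with non-missing values, and the protocol uses complete cases. The text specific to the primary follows the general sentence, and specific text ordinarily governs. This is persuasive, and it is the more natural reading. It does not remove the conflict: nothing says that the general rule yields, and the protocol and SAP name different populations for the main test.

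A second reply is that single imputation does not always shrink standard errors. That is correct, as Case 2 shows. The inflation in Case 1 depends on a fill method that the SAP does not state.

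A reader might infer that the 15% attrition in SAP 2.3 measures the exposure; Case 1 at 15% gives a single-test error of about 0.044. That does not apply to the primary. If 15% of outcomes were missing study-wide, the imputation methods specific to the primary in 6.2 would already be triggered. The 15% is a sample-size allowance, and 6.2 separately expects under 1% missing.

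For other binary outcomes, the available-data sentence in 4.1 competes with 6.2 as well, so it is not certain that they would be single-imputed. They are exploratory, and no confirmatory claim rests on them.

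**Conclusion.** The point stands as an unresolved conflict of rules, of minor to moderate severity. At or below 5% missing, the general rule in 6.2 and the available-data rule in 4.1 give different answers for the primary, and no sentence ranks them. The documents do not support a reading that type I error is inflated as planned. That would need the less natural reading of the SAP together with a particular fill method.

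If 6.2 were applied with random draws, and missingness were completely at random and equal between arms, one-sided error would rise from 0.025 to about 0.026 at 1% missing, which is negligible, and to about 0.031 at 5%. The larger exposure is a fixed fill with unequal missingness: about 0.08 against 0.022 at the final look in the assumed 5% against 0% pattern. For other binary outcomes, single imputation, if followed, would understate uncertainty or bias the comparison, depending on the fill.

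**What to change.** In SAP 6.2, delete the single-imputation sentence. State that the primary test uses observed outcomes in the pivotal mITT population, and align the protocol's complete-case wording with it.

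Run the multiple imputation already planned (20 datasets, combined by Rubin's rules) and the tipping-point analysis as sensitivity analyses at any level of missingness. If a trigger is kept, define it once: "In case, more than 5% study subjects with missing primary effectiveness endpoint" in 6.2 and the test-arm version in 8.4 are different conditions.

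For other binary outcomes such as readmission, use multiple imputation or available data, and say which.

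The cost is a few sentences in the SAP and a little more analysis work. No additional data or subjects are needed. The change should be made before unblinding.

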7. STATISTICAL METHODS

Statistical Analysis Plan (SAP)

There will be a formal SAP, separate from this Trial protocol. A formal SAP will be completed prior to database lock and the analysis of any Trial endpoints data. The SAP will detail the planned statistical analyses. The subsections below summarize the planned analyses.

Primary Outcome Endpoint

The primary outcome endpoint is to determine if the use of a protocolized strategy using advanced hemodynamic monitoring with Hypotension Prediction Index (HPI) software guidance for intraoperative hemodynamic management reduces postoperative complication rate in moderate- to high-risk non-cardiac surgery. The composite includes MACE (myocardial injury, stroke, non-fatal cardiac arrest, and death), AKI, and serious infections (pneumonia, deep and organ space surgical site infections, and sepsis).

THIS DOCUMENT CONTAINS CONFIDENTIAL AND PROPRIETARY INFORMATION OF EDWARDS LIFESCIENCES, LLC. IT MAY NOT BE REPRODUCED OR DISCLOSED WITHOUT PRIOR WRITTEN PERMISSION FROM EDWARDS LIFESCIENCES, LLC.
Edwards Lifesciences, Edwards, the stylized E logo, HemoSphere, Acumen, Acumen IQ, FloTrac, and ForeSight Elite oximetry Sensor are trademarks of Edwards Lifesciences Corporation.

Sample Size Justification

The goal of this study is to assess if the use of Hypotension Prediction Index (HPI) software guidance impacts the incidence of postoperative morbidity and mortality in the adult population undergoing moderate-to-high-risk noncardiac surgery (with a pressure monitoring with an arterial line). A relative reduction in the composite outcome within the treatment arm is expected. For a group sequential analysis, following the O'Brien and Fleming methodology, a sample size was calculated for a two-sample comparison of rates (two-sided). The hypothesis are as follows:

$$H_0: p_0 - p_1 \geq 0$$

$$H_1: p_0 \neq p_1$$

Assuming at least a 25% relative change in rate for the treatment (p_1) arm, a type I error (0.05), a power of 80%, and a reference rate of 0.31 (p_0) based on a meta-analysis^{6,10,14}, a sample size of 1426 subjects are needed. An additional 60 subjects may be included as roll-ins, which results in a total enrollment potential of 1486 subjects.

Analysis Populations

Modified Intent-to-treat (mITT)

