 Edwards	Revision Date: May 11, 2022		Rev	A	For Use Only by Affiliates of Edwards Lifesciences	Page 6 of 19
	Title	Statistical Analysis Plan for HP/ SMART-BP Trial				

estimation, and is supported by the integrated evidence from physician clinical experience, scientific publications, and previous clinical trial results.

The hypothesis setting for this study used in sample size estimation is:

$H_0: P_1 \geq P_0$

$H_1: P_1 < P_0$

where p_1 and p_0 are the proportions of composite endpoint in treatment arm and control arm, respectively.

Moreover, two interim analyses will be designed at 50% and 75% subject enrollment with 30-day follow-up data, to assess the composite endpoint (pooled event rate) between treatment and control arms. To determine when the trial can be stopped prematurely for effectiveness, the O'Brien-Fleming methodology¹⁶ was used to determine the stopping boundary (alpha spending function). The O'Brien-Fleming methodology preserves the overall type I error across all interim analyses¹⁶. The overall type I error used for this one tail hypothesis test study is 0.025. If the Z-statistics is close to boundary value but could not reject null hypothesis, possibly the study sample size will be reassessed for the purpose to achieve study objective.

With these trial parameter and hypothesis settings, and two designed interim analyses plus a final analysis, 1486 subjects (including 15% attrition, including a maximum of 60 roll-ins) are needed for this clinical trial. The sample size is estimated with PASS2021. The critical Z value and the corresponding p value for effectiveness boundary are displayed in the following table for interim analysis and final analysis. By the study objective and experiment design, in effectiveness analysis if the Z value calculated by the data available at each study stage (interim analysis and final analysis) is less or equal the critical Z value listed in effectiveness boundary column, the null hypothesis will be rejected, and the study stops for the study objective is achieved. To simplify the interim analysis decision making procedure, the lower limit of the reference arm accumulated subjects with complication, and the upper limit of treatment arm accumulated subjects with complication are designed by the study design parameters, the study arm accumulated sample size at each analysis stage, and effectiveness boundary (critical Z value) estimated by O'Brien-Fleming methodology.

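### The SAP judges its tipping-point analysis by a majority vote that never locates the tipping point and can call a fragile result robust when control-arm loss is heavier, and SAP 6.2 and 8.4 give conflicting triggers.

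*Combined protocol and SAP*

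**What the plan says.** SAP 4.1 and 8.1 run the primary comparison on pivotal mITT subjects, each included only where data are available. For endpoints missing not at random, SAP 6.2 says that "multiple imputed datasets are exported corresponding to all possible imputations", tests each one, and treats the finding as robust "if a reasonable majority of statistical hypothesis tests have the same outcome" as the test on the valid mITT data. It does not say how large a reasonable majority is, whether an imputation means a subject-by-subject 0/1 pattern or a pair of event counts, or whether the point of reversal is to be reported.

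The trigger appears twice. SAP 6.2: "In case, more than 5% study subjects with missing primary effectiveness endpoint". SAP 8.4: "If there are more than 5% study subjects with missing primary endpoint in test arm". SAP 6.2 refers the reader on to 8.4 without reconciling them.

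On how much may be missing, SAP 6.2 expects less than 1% of primary endpoints, from similar sponsor trials. SAP 2.3 states that "1486 subjects (including 15% attrition, including a maximum of 60 roll-ins) are needed".

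**The concern.** A tipping-point analysis should answer two questions: how far must the missing patients differ from the observed ones before the conclusion changes, and is that difference credible? A head count over every imputation answers neither. If subject-level patterns are counted, most lie near a 50% event rate in both arms, well above the planned 31% control rate. The vote is then dominated by a scenario nobody expects.

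At stake is the SAP's only analysis for informative loss. It could certify a result that disappears under a modest and realistic assumption. The meaning of a reasonable majority, and the way of counting, could also be settled after the results are known. With two triggers, it is unclear whether the missing-data sensitivity analysis is required when loss falls mainly in one arm.

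**Working it through.** **Inputs from the documents.** Pivotal N: the protocol's sample size section says "a sample size of 1426 subjects are needed", which at 1:1 is 713 per arm. Control event rate 0.31 (SAP 2.3). Final critical value 2.01404 in absolute terms (SAP 2.3). Test statistic (SAP 8.1): Z = (p0 − p1) / √[p0(1 − p0)/n0 + p1(1 − p1)/n1]. As written, this Z is positive when treatment is better, while the tabulated boundary is negative. I use the direction of benefit, so significance means Z ≥ 2.01404.

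**The plan's own figure.** "The overall type I error used for this one tail hypothesis test study is 0.025". The normal tails beyond 2.96259, 2.35898 and 2.01404 are 0.00153, 0.00916 and 0.02200, as tabulated. The joint crossing probability at 50%, 75% and 100% information is 0.0250. The boundary is sound.

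**Illustration (missing counts and observed events are assumptions).** 107 control and 71 treated endpoints missing, i.e. 15.0% and 10.0%, or 178/1426 = 12.5% overall. Both triggers fire.

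1. Observed data: 188/606 = 0.3102 against 166/642 = 0.2586. Difference 0.0517, standard error 0.02553, Z = 2.02: significant.
2. Vote by event-count pairs: 108 × 72 = 7,776 pairs, each tested once with 713 per arm; 55% stay significant.
3. Vote by subject-level patterns: each pair (i, j) weighted by C(107, i) × C(71, j) / 2^178; 76% stay significant.
4. Tipping point: give missing controls their own rate, 107 × 0.3102 = 33.2, rounded to 33, so control is 221/713. The observed treated rate implies 71 × 0.2586 = 18.4 events among missing treated patients.

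| Events among 71 missing treated | Rate | Treated total | Z |
|---|---|---|---|
| 18 | 25.4% | 184/713 | 2.18 |
| 20 | 28.2% | 186/713 | 2.06 |
| 21 | 29.6% | 187/713 | 1.99 |
| 22 | 31.0% | 188/713 | 1.93 |

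Significance goes at 21 events, 2.6 above expectation and below the control rate. A simple majority says robust by either count. A two-thirds majority says robust by patterns and not by pairs.

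**Why the pattern vote misleads here.** The centre of the patterns is 53.5 of 107 and 35.5 of 71 events. That adds 53.5 − 33.2 = 20.3 events to control beyond its own rate, but only 35.5 − 18.4 = 17.1 to treatment. At that centre, 241.5/713 against 201.5/713 gives Z = 2.29. Heavier control loss therefore makes the typical fill look better for treatment than the observed data do.

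**Equal loss, for comparison.** With 71 missing per arm, 199/642 against 164/642 gives Z = 2.17, a 51% pattern vote and tipping at 23/71 = 32.4%, above the control rate. One more observed treated event gives Z = 2.11, a 44% vote and tipping at 22/71 = 31.0%, at the control rate. Vote and plausibility check agree in both cases.

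**Triggers.** With 71 control (10.0%) and 35 treated (4.9%) missing, 106/1426 = 7.4%: SAP 6.2 fires and 8.4 does not. With 2% control and 6% treated missing, the overall figure is 4%: SAP 8.4 fires and 6.2 does not. The first split also shows the counting problem: at 199/642 against 176/678 (Z = 2.03), 90% of patterns but 59% of pairs stay significant.

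**The case against.** The strongest defence is that the vote is not empty. With equal missing numbers per arm (5% to 15% were checked), a simple-majority pattern vote passed a significant result exactly when its tipping rate exceeded the control rate. A reader might infer that the vote routinely certifies fragile results; the equal-loss cases do not support that.

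The SAP also says a reasonable majority, not a bare one, so a stricter threshold is open to it. That stands, but it does not rescue the rule: 76% of patterns agree in the unequal case, which passes two-thirds. If imputations are read as count pairs, the SAP already generates the full two-way grid and only its summary needs changing. This also stands and makes the repair easy.

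A reader might infer that the plan ignores control-arm loss when deciding whether to run the analysis. It does not: SAP 6.2 counts all study subjects, and only 8.4 is limited to the test arm. Nor is the 15% attrition in SAP 2.3 a forecast of missing primary endpoints. It is a sample-size allowance, and the only forecast is below 1%. It shows only that loss above 5% was allowed for.

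Finally, multiple imputation under random missingness and the FAS, PP and CC analyses are also planned, and none of these alters the primary test.

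**Conclusion.** The point holds in a limited form. The rule omits the quantity a tipping-point analysis exists to find, leaves its threshold and counting unit undefined, and under heavier control-arm loss can label a result robust that fails a modest assumption: 76% (patterns) or 55% (pairs) agreement, against loss of significance at 29.6% events among missing treated patients. Separately, the two triggers contradict each other.

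The illustration rests on assumed missing counts and events, missing controls at their own observed rate, the unpooled Z of SAP 8.1 and the final boundary. The problem arises when the observed Z is close to that boundary. For a result of about the planned size it vanishes: with 71 control and 35 treated missing and 199/642 against 158/678 (Z = 3.15), virtually all patterns agree and tipping needs 29/35 = 83% events among missing treated patients. Only a conditional sensitivity analysis is affected, so this should be corrected but does not threaten the primary inference.

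**What to change.** In SAP 6.2, replace the vote with a two-way grid of event rates (or counts) among missing subjects, varied separately by arm. Report the boundary along which Z crosses 2.014 in the direction of benefit. Prespecify, before unblinding, what makes the boundary implausible. One workable criterion is that the result must survive missing treated patients having the observed control rate, with missing controls at their own rate. The illustration above would fail it (22/71, Z = 1.93).

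State one trigger in both SAP 6.2 and 8.4: more than 5% missing overall or in either arm. That would fire in both of the split-loss examples. The cost is SAP wording and one table; no data collection or sample size changes.
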